## LIST OF ABBREVIATIONS

The following abbreviations describe terms, documents and study personnel used in the conduct of this study protocol.

AD	Alzheimer's disease
AE	Adverse Event/Adverse Experience
ARWMC	Age-Related White Matter Change
CAD	Coronary Artery Disease
ccf-mtDNA	Circulating cell-free mitochondrial DNA
CR	Cardiac Rehabilitation
CRF	Case Report Form
CTS	Clinical Trial Services
ICH	International Conference on Harmonization
IP	Investigational Product
pCRF	Paper Case Report Form
GCP	Good Clinical Practice
GSH	Glutathione
ICF	Informed Consent Form
MCI	Mild Cognitive Impairment
NAC	N-acetylcysteine
NINDS-CSN	National Institute of Neurological Disorders and Stroke-Canadian Stroke Network
OS	Oxidative Stress
PHI	Personal Health Information
PI	Principal Investigator
PIGF	Placental Growth Factor
PM	Product Monograph
QI	Qualified Investigator
REB	Research Ethics Board
SAE	Serious Adverse Event/Serious Adverse Experience
SOP	Standard Operating Procedure
SRI	Sunnybrook Research Institute
SUADR	Serious and Unexpected Adverse Drug Reaction
VCI	Vascular Cognitive Impairment

## PROTOCOL SUMMARY

Protocol Title (Short Title)	Efficacy and Safety of N-acetylcysteine in patients with mild vascular cognitive impairment (MOVE-IT)
Protocol Number	1.9
Phase	II
Study Design	Randomized, double-blind, placebo-controlled parallel group
Study Duration	5 years
Setting	Single-centre
Sample Size	60
Main Inclusion Criteria	Males or females aged 55-85 years, with mild vascular cognitive impairment (VCI), who are enrolled in a supervised cardiac rehabilitation program.
Primary Outcome(s):	In patients with mild VCI, those randomized to NAC (2,400 mg/day) will demonstrate greater improvement in executive function over 24 weeks as compared to those randomized to placebo.
Secondary Outcome(s):	In patients with mild VCI, those randomized to NAC (2,400 mg/day) will demonstrate greater improvement in processing speed, memory and working memory over 24 weeks as compared to those randomized to placebo.
Investigational Product and Planned Use	
N-acetylcysteine (NAC) Natural Health Products Directorate (NPN #: 80004844).
 
Patients will be randomized to receive NAC (four 600 mg capsules given as 2 capsules in the morning and 2 capsules in the evening) or matching placebo capsules. The initial NAC dosage will be 600mg/day (one 600mg capsule in the morning) for the first week, followed by 1,200 mg/day (one 600 mg capsule in the morning, one 600mg capsule in the evening) for the second week, followed by 1,800 mg/day (two 600mg capsules in the morning, one 600mg capsule in the evening) for third week, followed by 2,400mg/day (two 600mg capsules in the morning, two 600mg capsules in the evening) for the following 21 weeks.

Statistical Analysis:	Differences in executive function composite z scores between the groups at 24 weeks will be compared between groups using a two sample two sided t-test. A linear mixed model will be run to compare the rate of change in the executive function measure over time.

## 2 INTRODUCTION

This study document is the protocol for research involving human participants. This study is to be conducted according to Canadian and international standards, and in compliance with the protocol, International Conference on Harmonisation Good Clinical Practice E6 (ICH-GCP), World Medical Association Declaration of Helsinki: Ethical Principles for Medical Research Involving Human Participants, as well as applicable regulatory and institutional requirements and research policies.

### 2.1 Background and Rationale

#### 2.1.1 *Vascular cognitive impairment-no dementia*

The prodromal stage of major neurocognitive disorders has become the current target for interventional research, as this stage may provide an optimal therapeutic window for neuroprotection. Mild vascular cognitive impairment is a prodromal stage defined by early cognitive deficits due to cerebrovascular disease that are not severe enough to be classified as dementia and is the most prevalent form of vascular cognitive impairment (**VCI**) among those aged 64 to 84 years. Probable mild VCI is characterized by neuroimaging findings confirming vascular pathology; clinical symptoms indicating vascular disease in the absence of these neuroimaging findings is categorized as possible mild VCI.

Consistent with the recognition of vascular contribution to cognitive impairment and dementia, those with **coronary artery disease (CAD)** are particularly at risk for mild VCI. Clinical trials evaluating the efficacy of cholinesterase inhibitors and memantine, as well as primary prevention trials to control traditional vascular risk factors have demonstrated no significant benefit of these interventions in the prodromal stage. Regular exercise is promising, but has variable efficacy on cognition, particularly in the preclinical stages. There is currently no effective treatment for those at increased risk for dementia.

#### 2.1.2 *Oxidative stress*

Oxidative stress (**OS**) plays a major role in age-related neurodegeneration. Cumulative reactive oxygen species cause cellular damage, mitochondrial dysfunction and impair the DNA repair system, all of which are key factors involved in the propagation of neuronal injury leading to apoptosis. Consistent with this, increased oxidative damages have been implicated as early events in the evolution of the neurodegenerative processes. Similarly, decreased levels of glutathione (**GSH**), the primary antioxidant in the brain, are observed in patients with neuropsychiatric disorders. Antioxidant supplementation has been proposed for dementia prevention and therapy. Observational and epidemiological studies with dietary or supplemented antioxidants showed benefits, although findings from controlled trials have been mixed. Of those studies, therapy with the antioxidant N-acetylcysteine (**NAC**) showed promise, consistent with action as an effective GSH precursor.

Importantly, emerging evidence suggests that altered OS might represent an early event in the neurodegenerative process. A recent meta-analysis showed that lipid peroxidation was significantly elevated while a range of antioxidant levels were depleted in mild cognitive impairment (**MCI**) patients. OS may be particularly important in mild VCI as cerebral

hypoperfusion can cause ischemia- and inflammation- related increases in OS. Our pilot data showed that high OS predicted less cognitive improvement following a 6-month exercise intervention, suggesting that elevated OS levels might interfere with the benefit of exercise on cognition.

### ***2.1.3 The therapeutic potential of antioxidant supplementation N-acetylcysteine for cognition***

GSH depletion plays an important role in OS-mediated neuronal loss. As such, increasing central GSH has been proposed as a promising therapeutic strategy in Alzheimer's disease (AD). NAC protects the cells against OS damage by increasing the endogenous intracellular GSH level. NAC bioavailability, metabolism and plasma levels have been studied in humans. NAC has been shown to cross the blood brain barrier and accumulate in the central nervous system, where it lowers lipid peroxidation and beta-amyloid deposition. NAC also protects neuronal function and improves cognitive deficits by decreasing acetylcholinesterase activity and increasing acetylcholine levels. Clinical studies in patients with AD suggest that NAC may have pro-cognitive effects. Patients with mild to moderate AD treated with NAC for 24 weeks showed significant improvement in performance on the Letter Fluency Task and Wechsler Memory Scale Immediate Number Recall. In a 12-month small open label trial, a vitamin/nutraceutical formulation containing NAC produced a significant effect on executive function in individuals with early stage AD and MCI. However, to date, no studies have evaluated the effects of NAC on cognition in patients with mild VCI.

Those with mild VCI show deficits across all cognitive domains, with greater impairment typically being found in executive function. Impairment in cognitive subdomains of memory, processing speed and working memory have also been found in mild VCI populations. Our recent pilot data showed CAD patients with possible mild VCI had elevated levels of OS compared to CAD controls. In addition, higher baseline ratios of late to early lipid peroxidation markers (8-isoprostanate (8-ISO) to lipid hydroperoxides (LPH) ratio) predicted less improvement in executive function following an exercise intervention. Since OS damage occurs early in the pathogenesis of the disease and might precede other neuropathological alterations, an antioxidant intervention would be most beneficial if started before the onset of symptomatic dementia. We propose to combine the synergistic effects of NAC supplementation and exercise to increase the efficacy of each individual intervention to reduce OS and improve cognitive performance in patients with mild VCI. If successful, this study will demonstrate that NAC, a widely available and safe supplement, can improve cognitive outcomes in patients at high risk of cognitive and functional decline.

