
## 7.4 Statistical Analyses

All analyses will be performed using current versions of SPSS and SAS (SAS Institute, Cary, NC, USA). The intention-to-treat analyses will be based on data from all patients who undergo randomization, meet the inclusion criteria for the study, receive the trial medication at least once, and undergo at least baseline observation. Descriptive statistics will be calculated for composite z-scores for executive function, memory, and speed of processing. Categorical variables will be summarized using counts and percentages. Continuous variables will be compared between groups using two sample two sided t-tests (or Wilcoxon rank sum tests for non-normal data), whereas categorical variables will be compared between groups using chi-square analyses or Fisher's exact tests.

Primary Hypothesis: Differences in executive function composite z scores between the groups at 24 weeks will be compared between treatment groups using a two sample two sided t-test. A linear mixed model will be run to compare the rate of change in the executive function measure over time (baseline, 12- and 24-weeks). The linear mixed model is selected as it can accommodate missing data in subjects. The effects of age, sex, BMI, total years of education, VO2 peak, physical activity levels, serum homocysteine, will be included as possible covariates. The same analyses will be repeated with the composite z-scores of the other cognitive domains as repeated variables to test for the effect of NAC treatment on the secondary outcome measures.

Secondary Hypotheses: A linear mixed model will also be used to test the hypothesis that patients with mild VCI treated with NAC will show a greater reduction in 8-ISO/LPH ratio over 24 weeks of treatment. The early to late stage lipid peroxidation marker ratio will be inputted as the repeated variable, and treatment group will be added as a fixed factor. The effects of group by time interaction will be evaluated to indicate significant effects of NAC in reducing oxidative stress markers as compared to placebo. APOE4 genotype status, BMI, VO2 peak, and sex will be added as covariates. Similar analyses will be conducted separately with GPx, GR and GST inputted as the repeated variable. Logistic regression analyses will be performed to examine whether baseline severity of WMH is a significant predictor of cognitive response to NAC treatment at 24 weeks, adjusting for the same covariates.

Exploratory Hypothesis:

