### **7.5 Power Calculation**

Based on a published randomized placebo-controlled trial in patients with probable AD, oral NAC treatment resulted in a significant improvement in executive function in the active treatment group ( $p= 0.008$ ) but not in placebo. Our preliminary analysis of MOVE-IT blinded data ( $n=30$ ) was used to provide an updated estimate of the standard deviation ( $SD=0.55$ ) of executive function Z-scores in our population, controlling for education. Based on this, a sample size of 42 (21 in each group) will provide 80% power, at alpha of 0.05, to detect a medium effect size in a linear mixed model with a hypothesized intra-cluster correlation of 0.1. The sample size calculation was carried out using PASS Version 12 (Kaysville, Utah.). Due to the uncertainties of COVID-19 pandemic, a generous drop-out rate was used. To account for a drop-out rate of 42%, we will inflate the sample size to 60.

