## 14 SUPPLEMENTAL MATERIALS

### Appendix A: Study Assessment Schedule

Table 1. Schedule of Assessment

Visit/phone calls (Weeks)	-5	-1	0*	1*	2*	3*	4*	8*	12	16*	20*	24
			± 14 days	± 14 days	± 2 days	± 2 days	± 2 days	± 7 days	± 7 days	± 7 days	± 7 days	± 7 days
Informed Consent	X											
Inclusion/Exclusion Criteria	X	X	X									
Demographics												
Age, gender, education, language	X											
Concomitant medications	X		X					X	X	X	X	X
Vascular risk factors	X											
Anthropomorphic parameters			X 						X 			X 
Medical, Surgical, and Psychiatric History	X											
Cognitive Outcomes												
NINDCS-60 minute cognitive assessment.	X									X		X
MoCA, AES, MBI-C	X									X		X
Dietary Intake												
Food Diary			X					X	X	X	X	X
Fasting Blood Draw												
GSH markers: GPx, GR, GST			X							X		X
Ccf-mtDNA & OS markers: LPH, 4-HNE, 8-ISO, MPO, oxylipins			X							X		X
APOE4 genotype			X									
S100B, PIGF			X						X			X
Exploratory Neuroimaging Outcome												
MRI and MRS		X										
Exercise Intervention Outcome												
VO 2 peak			X 							X 		X 
IP Administration												
Drug Dispensing			X					X	X	X	X	X
Compliance Measures												
Capsule Count								X	X	X	X	X
Safety Outcomes												
Heart rate, blood pressure			X					X	X	X	X	X
Plasma electrolyte panel and homocysteine level		X										X
Phone call				X	X	X						X 
Adverse events review			X	X	X	X	X	X	X	X	X	X

1. Collected from TRI on the visit date, as available. 2. At least 32 hours after the final dose.

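### Baseline 8-ISO/LPH, which predicted executive-function gain in the sponsor's pilot, is named in no model of cognitive change in section 7.4

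*Combined protocol and SAP*

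**What the plan says.** Section 2.1.2 says of the sponsor's pilot that "high OS predicted less cognitive improvement following a 6-month exercise intervention, suggesting that elevated OS levels might interfere with the benefit of exercise". Section 2.1.3 is more specific: the predictor was the baseline ratio of a late to an early lipid-peroxidation marker, 8-ISO to LPH, and higher values "predicted less improvement in executive function following an exercise intervention". Every participant in this trial is in cardiac rehabilitation, and executive function is the primary outcome (sections 3.1 and 4.1).

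The marker row "Ccf-mtDNA & OS markers: LPH, 4-HNE, 8-ISO, MPO, oxylipins" is scheduled at week 0 in Appendix A and at week -1 in Appendix B, then at two later visits.

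For cognition, section 7.4 plans an unadjusted two-sided t-test at week 24 and a linear mixed model over baseline, week 12 and week 24. The candidate covariates are age, sex, BMI, education and VO2 peak, and the list ends with "physical activity levels, serum homocysteine, will be included as possible covariates". No lipid-peroxidation marker is among them. In the secondary analyses, 8-ISO/LPH is the outcome. In the exploratory analyses it is compared between the possible and probable subgroups, and oxidative-stress markers are related to ccf-mtDNA and PIGF.

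**The concern.** This is the one covariate for which the sponsor reports its own evidence of predicting the primary outcome under the same background treatment, exercise. It is collected before treatment and is then not used to explain cognitive change. Two things are at stake.

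- **Precision.** Outcome variation that a collected baseline variable might explain stays in the residual.
- **The moderator question.** The rationale suggests that high oxidative stress blunts the gain from exercise and that NAC relieves this. It is natural to ask whether the NAC effect depends on the baseline ratio. Section 7.4 names no such analysis, so one chosen after unblinding would be post hoc. By contrast, white-matter severity is named in advance as a predictor of response.

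**Working it through.** **1. Where oxidative-stress measures meet cognition in the plan**

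| Planned analysis | Does it cover baseline 8-ISO/LPH and cognitive change? |
|---|---|
| Week-24 t-test | No covariates |
| Cognitive mixed model | Seven candidate covariates, none of them the ratio |
| MPO regression | Different marker; cross-sectional at baseline |
| Brain glutathione by time | Different marker; no treatment interaction; needs MRS, while section 7.1 admits patients who cannot have MRI |
| Oxylipins with mood and cognition | Different marker |
| White-matter logistic regression | Different predictor; ratio not among the covariates |
| Logistic regression for predictors of response | Open list; names only demographics and compliance |

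**2. The plan's own sample size**

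Section 7.5 states that "a sample size of 42 (21 in each group) will provide 80% power, at alpha of 0.05", and that this is "to detect a medium effect size in a linear mixed model with a hypothesized intra-cluster correlation of 0.1". The SD is 0.55. The effect has no number, so 42 cannot be confirmed. With n per arm = 2(1.96 + 0.84)² × [1 + (m - 1)ρ] / (m d²) and ρ = 0.1:

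- m = 3 visits, d = 0.5: 25.1, so 26 per arm (52 in total)
- m = 3, d = 0.55: 20.8, so 21 per arm (42)
- m = 4, d = 0.5: 20.4, so 21 per arm (42)

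This formula concerns a mean over repeated visits. The figures in step 4 concern a single two-group comparison and should not be set against the plan's 80%.

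**3. Variance removed**

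Let r be the partial correlation of baseline log(8-ISO/LPH) with executive-function change. The documents give no value, so r is assumed. The residual variance is multiplied by 1 - r² and the standard error by √(1 - r²). Charging one degree of freedom at N = 42 multiplies the variance by about 1 + 1/38.

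| r | Variance removed | SE reduction | Net variance factor, N = 42 |
|---|---|---|---|
| 0.1 | 1% | 0.5% | 1.02 |
| 0.2 | 4% | 2.0% | 0.99 |
| 0.3 | 9% | 4.6% | 0.93 |
| 0.4 | 16% | 8.3% | 0.86 |
| 0.5 | 25% | 13.4% | 0.77 |

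**4. Power of a two-group comparison**

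Two-sided 0.05, noncentral t with noncentrality d√(n/2)/√(1 - r²), one degree of freedom lost for the covariate, and d = 0.5 assumed for a medium effect.

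| n per arm | No covariate | r = 0.1 | r = 0.3 | r = 0.5 |
|---|---|---|---|---|
| 21 | 35% | 36% | 38% | 45% |
| 30 (no drop-out) | 48% | 48% | 51% | 59% |

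These apply to change or to a baseline-adjusted week-24 score, because the pilot relation was with improvement. For raw week-24 scores the correlation would be r√(2(1 - c)), where c is the baseline-to-week-24 correlation, if the ratio is unrelated to the baseline score and variances are equal. At an assumed c = 0.7, r = 0.3 to 0.5 becomes 0.23 to 0.39, and the variance removed is 5% to 15%.

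**5. Form of the covariate in the mixed model**

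A baseline covariate entered only as a main effect shifts all of a patient's visits equally, so it drops out of the within-patient contrast behind group by time. A simulated three-visit model with 60 patients gave an SE of 0.229 for group by week 24, with or without the main effect, and 0.222 with ratio by visit at r = 0.33. That is (0.229/0.222)² = 1.064, worth about 6% more patients.

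**6. Power of a treatment-by-ratio interaction**

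The SE is about 2/√N outcome SDs per SD of the ratio, with N - 4 degrees of freedom. For interactions of 0.3 to 0.7 SD per SD:

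- N = 42: 16% to 60%
- N = 60: 21% to 76%

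On the normal approximation, 80% power needs (1.96 + 0.84) × 2/√N, which is 0.86 at N = 42 and 0.72 at N = 60.

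**The case against.** The best case for the plan is that this is a choice among prognostic covariates. Seven candidates are already listed for about 42 evaluable patients, and leaving out an eighth of unknown strength does not bias a randomised comparison. The pilot is reported without a correlation, sample size or interval. If r is 0.1, the lost degree of freedom cancels the gain. All of this stands, and it keeps the precision argument modest.

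Two stronger readings are tempting, and the documents support neither.

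- A reader might infer that oxidative stress is absent from every cognitive analysis. It is not. MPO, listed in the same schedule row as 8-ISO and LPH, is modelled against baseline cognition. Brain glutathione by time is modelled against change in all four domains. Oxylipins are explored alongside cognition.
- A reader might infer that the trial's premise goes untested. Section 7.4 tests NAC on executive function and NAC on 8-ISO/LPH. The documents do not say that NAC works only, or mainly, where the ratio is high. Section 2.1.3 says the pilot patients with possible mild VCI had elevated oxidative stress as a group. The comparison of possible with probable mild VCI, where the latter is expected to have higher oxidative stress, is a partial proxy for moderation.

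What remains is narrower. None of these analyses relates the baseline ratio itself to cognitive change or to NAC response, and the open predictor list in the response model is not pre-specification.

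**Conclusion.** The concern holds in a limited form. Baseline 8-ISO/LPH has the sponsor's own pilot evidence behind it and is collected before dosing, yet it is not a named covariate, predictor or effect modifier in any planned model of cognitive change. The cost is some precision and a missing pre-specified look at the prognostic and moderator link; it is not bias.

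The precision gain runs from negligible at r = 0.1, through about 9% of residual variance at r = 0.3, to 25% at r = 0.5. At d = 0.5 and 21 per arm that is 35% power rising to 38% or 45% at the last two values. Both r and d are assumptions, and the pilot relation was seen with exercise, not under NAC.

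A reader might also expect an interaction test to show whether a null result hides benefit confined to patients with high oxidative stress. At these sample sizes it cannot settle that: a non-significant interaction would leave the question open. Its value is a pre-specified estimate with an interval.

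**What to change.** Amend section 7.4 before unblinding:

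1. Add baseline log(8-ISO/LPH) and its interaction with visit to the executive-function mixed model. A main effect alone does not help the group-by-time test.
2. Use it as a covariate in a week-24 comparison that also adjusts for the baseline executive-function score.
3. Repeat both for the other cognitive domains.
4. Name one exploratory analysis, treatment by baseline log(8-ISO/LPH) on week-24 executive function. Report the estimate with its confidence interval and state that power is low.
5. Define the ratio once as late over early. Section 3.2 has it that way round, while one sentence in section 7.4 describes the reverse; on the log scale this changes only the sign.

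The cost is protocol or SAP wording, one or two degrees of freedom, and a stated rule for patients without a baseline sample, such as imputing the baseline value. No new visit or assay is needed.

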### 3 STUDY OBJECTIVES

#### 3.1 Primary Objective

As highlighted above, NAC preferentially improved executive function. Our primary goal is to evaluate the therapeutic potential of direct antioxidant supplementation using **NAC** to enhance the effect of exercise on executive function in patients with mild VCI. We hypothesize that:

- In patients with mild VCI, those randomized to NAC (2,400 mg/day) will demonstrate greater improvement in executive function over 24 weeks as compared to those on placebo.

Executive function will be based on verbal fluency and trail test A & B found in the 60-minute battery recommended by the National Institute of Neurological Disorders and Stroke-Canadian Stroke Network (**NINDS-CSN**) harmonized standards. It is the cognitive domain most frequently impacted in mild VCI, and it reflects white matter lesion burden, the key neuroimaging finding defining probable mild VCI. The 24 week treatment duration was chosen based on a previous clinical trial of NAC in patients with probable AD. The daily dose is consistent with the upper dosing range in published clinical trials, in which oral NAC supplementation was investigated in a variety of populations including AD, where evidence of tolerability and efficacy were observed.

